14.4. Study Documentation

The investigator must prepare and maintain adequate and accurate case histories designed to record all observations and other data pertinent to the study for each research participant. This information enables the study to be fully documented and the study data to be subsequently verified.

Original source documents supporting entries in the case report forms include but are not limited to hospital records, clinical charts, laboratory and pharmacy records, recorded data from

automated instruments, microfiches, photographic negatives, microfilm or magnetic media, and/or x-rays.

14.5. Records Retention

All study-related documents must be retained for the maximum period required by applicable federal regulations and guidelines or institutional policies.

14.6. Multi-center Guidelines

N/A

15. STATISTICAL CONSIDERATIONS

15.1. Study Design/Endpoints

This is a single arm, single stage phase II study to evaluate the response to the novel PARP inhibitor ABT-888 in combination with TMZ. Eligible subjects have unresectable or stage IV metastatic breast cancer with measurable disease according to RECIST. Subjects must have at least 1 prior therapy for metastatic disease, with no maximum. Subjects in the expansion cohort may have any number of prior chemotherapy regimens for metastatic disease, with no limit on total number of lines of prior therapy. All histologic subtypes of breast cancer are eligible. Subjects will receive study treatment with ABT-888 twice each day on days 1-7 and TMZ once each day on days 1-5 of each 28 day cycle. The primary endpoint of the study is the objective response rate. Secondary endpoints are the clinical benefit rate (CR+PR+stable disease > 16 weeks), progression free survival, and safety. Additional correlative exploratory endpoints will be carried out on archived tumor sample and blood.

There are only few small reports of TMZ for metastatic breast cancer. The reported response rate to TMZ monotherapy is poor, with 0 responses in 18 patients³². TMZ in combination with platinum in metastatic breast cancer with brain metastases was 6 of 15 patients³³, and 2 studies of TMZ monotherapy in breast cancer with brain metastases demonstrated no responses^{34, 35}. A growing literature of preclinical studies of TMZ and ABT-888 (and other PARP inhibitors) provides strong support for the hypothesis that the combination will demonstrate significant clinical activity.

Primary Endpoint

The primary endpoint of this study is to determine the objective response rate (ORR) of ABT-888 and TMZ in metastatic breast cancer.

TMZ has no demonstrated monotherapy activity in breast cancer at this time. Therefore a true response rate of 20% associated with the combination of ABT-888 and TMZ in this heavily pretreated heterogeneous population would be considered to be of considerable clinical benefit worthy of further study. On the other hand, a true response rate of 5% to this combination would be considered to be of no clinical interest. The combination will be considered worthy of further research if at least 5 of the 41 subjects have a confirmed PR or CR. With this design, if the true response rate is 5% then there will be a 0.05 (alpha=0.05) chance of deeming the combination worthy of further research. If the true response rate is 20%, then there will be a 0.93 (beta=0.07) chance of deeming the combination worthy of further research.

A 90% confidence interval (CI) will be calculated for the true response rate. The 90% CI will be 5 to 24% if 5 of the 41 patients have a confirmed response; it will be 8 to 30% if 7 of the 41 have a confirmed response; it will be 12 to 35% if 9 of the 41 patients have a confirmed response.

Expansion Cohort

The primary endpoint of the expansion cohort is to further characterize the ORR of ABT-888 and TMZ in metastatic breast cancer in patients with known deleterious mutations in BRCA1 or BRCA2. Based on preliminary subset analysis from the primary study, among 41 patients enrolled there were 8 patients with known mutations in BRCA1 or BRCA2. The response rate among the 8 BRCA1 and BRCA2 mutation carriers was 50% (4/8; 1 CR, 3 PR) and the clinical benefit rate (CR+PR+SD>16 weeks) is 62.5% (5/8). The patient with SD has had continued reduction in tumor size from 8% to 24% at the 4th cycle and remains on study.

Based on the preliminary response data above, in the population of BRCA1 and BRCA2 carriers a true response rate of 45% would be considered of considerable clinical benefit. A true response rate of 15% in this population would be considered of little clinical interest. If at least 7 of the 20 subjects have a confirmed PR or CR the study will be deemed a success. With this design, if the true response rate is 15% then there will be a 0.025 (1-sided alpha=0.025) chance of deeming the combination worthy of further research. If the true response rate is 45%, then there will be a 0.87 (beta=0.13) chance of deeming the combination worthy of further research.

15.2. Sample Size/Accrual Rate

A total of 41 patients who receive at least one cycle of study drug will be enrolled.

Subjects who discontinue study participation after enrollment but before receiving one cycle of study drug will be replaced with an additional subject. Subjects who receive at least one cycle of study drugs but who never have follow-up tumor measurements done will be counted as non-responders.

Approximately 2-3 patients per month, minimally, are expected to accrue over 18 months for a total of 41 subjects. However, due to investigator and patient interest, accrual may be rapid between all DFHCC sites.

In the expansion cohort a total of approximately 20 patients are planned to be enrolled, with up to 22 allowed, in case of possible rapid accrual over a short period of time. This will allow patients who may have signed consent prior to formal administrative closure of the trial to enroll. Approximately 5 patients per month are expected to accrue over 4 months.

15.3. Analysis of Secondary Endpoints

Secondary Endpoints

All patients who receive at least 1 cycle of study drugs will be considered evaluable for clinical benefit analysis (CR+PR+SD>16wks); those who lack tumor measurements will be counted as non-responders. Patients who develop early disease progression, regardless of duration of study treatment, prior to response evaluation will be considered to have progressed on study. The 90% confidence interval will be calculated.

Progression free survival (PFS) will be defined as the time from enrollment until disease progression, death, or date of last patient contact. Patients alive and free from disease progression (including being free of CNS progression) will be considered censored. All other patients will be considered to have experienced an event. Risk for PFS-event will be estimated according to the method of Kaplan and Meier and confidence curves will be estimated by the Greenwood method.

Analysis for safety will be completed for all subjects who receive at least 1 dose of either ABT-888 and/or TMZ. Subject incidence rates of all adverse events will be tabulated organ system class, preferred term, and severity. Tables and/or narrative descriptions of deaths occurring while on trial and other serious adverse events and early withdrawals due to adverse events will be provided.

All reported AEs will be assigned to an organ system class and preferred term according to MedDRA AE preferred term dictionary. The number and percentage of subjects reporting adverse events (categorized as all, serious and related) will be tabulated.

Summary statistics for certain laboratory evaluations and other recorded findings will be generated. Summary statistics for recorded toxicities according to CTCAE 3.0 may be generated.

The DFHCC DSMC will also monitor this study as described in Section 13.2.

Exploratory Endpoints

Summary statistics will be presented for the total number of subjects in each of the following subgroups of breast cancer, and the number of subjects responding in each group: triple negative (<1% ER, <1%PR, and HER2 negative), HER2 positive (any ER/PR status, HER2 3+ by IHC or positive by FISH), or Endocrine positive (HER2 negative and ER positive and/or PgR positive).

Summary statistics will be presented for the total number of patients with brain metastases at baseline, the response of those patients having RECIST-measurable brain metastases, the response of non-CNS disease in those patients, and narrative descriptions of those patients.

The BRCA mutation status, the BRCA methylation status, and the BRCA expression level in archived tumors will be determined and presented as summary statistics.

Exploratory studies to evaluate the number of Circulating Tumor Cells at baseline and prior to cycle 2 will be presented in summary tables.

Summary tables describing the presence of any oncogene mutations identified with multiplex mutation analysis will be presented.

Patients who experience CNS-only progression and remain on study according to Section 6.6 will be coded as having a progression at the time of their CNS-only progression, but the amount of time they remain on treatment without further progression will be reported for descriptive purposes only.

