6.4. Duration of Therapy

Duration of therapy will depend on individual response, evidence of disease progression and tolerance. In the absence of treatment delays due to adverse events, treatment may continue indefinitely or until one of the following criteria applies:

- Disease progression (note: see Section 6.6 for CNS-only progression),
- Intercurrent illness that prevents further administration of treatment,
- Unacceptable adverse event(s),
- Participant decides to withdraw from the study,
- General or specific changes in the participant's condition render the participant unacceptable for further treatment in the opinion of the treating investigator, or
- Study drug becomes unavailable due to manufacturer or other causes.

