6.5. Duration of Follow Up

Participants will be followed for two years after removal from study. . Participants removed from study for unacceptable adverse events will be followed until resolution or stabilization of the adverse event. Patients will be followed off study by their primary treating physician. At the time of informed consent, patients will be asked for permission to contact the patient or their family in the future after coming off therapy to determine patient outcome or if any relevant follow up issues arise from the clinical or exploratory endpoints.

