11.1.5. Duration of Response

Duration of overall response: The duration of overall response is measured from the time measurement criteria are met for CR or PR (whichever is first recorded) until the first date that recurrence or PD is objectively documented, taking as reference for PD the smallest measurements recorded since the treatment started.

Duration of overall complete response: The duration of overall CR is measured from the time measurement criteria are first met for CR until the first date that recurrent disease is objectively documented.

Duration of stable disease: Stable disease is measured from the start of the treatment until the criteria for progression are met, taking as reference the smallest measurements recorded since the treatment started.

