15.4. Reporting and Exclusions

15.4.1. Evaluation of toxicity.

All subjects who receive at least one dose of study drug (ABT-888 and/or TMZ) will be considered evaluable for toxicity from the time of their first treatment.

Subjects who enroll but do not receive any study treatment will not be considered evaluable for toxicity.

15.4.2. Evaluation of response.

All subjects who register to participate in the study and receive at least one cycle of study drug will be assessed for response to treatment even if there are major protocol treatment deviations or if they are ineligible. Each participant should be assigned one of the following categories: 1) complete response, 2)

partial response, 3) stable disease, 4) progressive disease, 5) early death from malignant disease, 6) early death from toxicity, 7) early death because of other cause, or 9) unknown (not assessable, insufficient data). By arbitrary convention, category 9 usually designates the "unknown" status of any type of data in a clinical database.

All participants who met the eligibility criteria, except those who received no study medication, will be included in the main analysis of the response rate. Participants in response categories 4-9 should be considered to have a treatment failure (disease progression). Thus, an incorrect treatment schedule or drug administration does not result in exclusion from the analysis of the response rate. Patients who did not receive any dose of study drug will not be included in the response evaluation.

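### Section 15.3 runs PFS to last patient contact, so a patient who leaves without documented progression can stay at risk long after the last scan

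*Combined protocol and SAP*

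**What the plan says.** Section 15.3 defines the interval: "Progression free survival (PFS) will be defined as the time from enrollment until disease progression, death, or date of last patient contact". It continues: "Patients alive and free from disease progression (including being free of CNS progression) will be considered censored", and then: "All other patients will be considered to have experienced an event". Estimation is by Kaplan-Meier with Greenwood's method, and CNS-only progression is expressly coded as progression. No sentence names the last tumour assessment as the censoring date. None expressly places a living patient whose progression status is unknown.

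Other sections make such patients possible. Section 6.4 lists reasons for stopping other than progression, among them adverse events, intercurrent illness and "Participant decides to withdraw from the study". Table 10.1 schedules scans every two cycles (8 weeks) and a last one at Off Study. Section 6.5 then says "Participants will be followed for two years after removal from study" and "Patients will be followed off study by their primary treating physician". Section 13.1.2 has a follow-up/survival form completed after a visit or a call. No scan schedule covers these two years. By contrast, section 11.1.5 measures duration of response "until the first date that recurrence or PD is objectively documented".

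**The concern.** Kaplan-Meier treats a censored patient as known to be event-free up to the censoring date. A telephone call that finds the patient alive says nothing about the tumour. If that call sets the date, the patient stays in the risk set through a period in which progression could not be seen. Later progressions by other patients are divided by too large a number at risk, and the curve flattens.

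PFS is a secondary objective in both cohorts (section 2.3), and section 3.3 says the expansion data are to support later trials. A tail held up by unscanned patients could be taken for durable disease control.

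**Working it through.** The plan gives no PFS median, landmark rate, event count or test, so there is no figure of its own to reproduce.

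**Length of the gap.** Two years of follow-up against an 8-week scan interval is 104 / 8 = 13 intervals without a required scan.

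**Mechanism by hand (invented data).** Take 41 patients. Eight leave after a clear week-8 scan, with no later progression or death recorded. The other 33 progress at scans: 14 at week 8, 8 at week 16, 5 at week 24, 3 at week 32 and 3 at week 40. With S(t) = product of (1 - events / at risk):

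- Leavers censored at the last scan (week 8): S(24) = 27/41 x 11/19 x 6/11 = 0.208, and S(48) = 0.
- Leavers censored at last contact (week 8 + 104 = 112): S(24) = 27/41 x 19/27 x 14/19 = 14/41 = 0.341, and S(48) = 8/41 = 0.195.

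The median is week 16 both ways. The difference lies in the tail.

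**Size by simulation.** From the documents: n = 41 or 20, 8-week scans, an Off Study scan, and contact for up to 24 months after exit (6 and 12 months also run). Assumed: exponential PFS, exponential post-progression survival with median 10 months, leaving independent of prognosis, 5-20% leaving without documented progression, and 0, 50 or 100% of later progressions captured. There were 1,500 replicates per setting. The reference is the same patients scanned every 8 weeks throughout.

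Excess in 6-month PFS under the literal rule, in percentage points (n = 41, true median 2 months, reference about 14.7%, sampling SD 5.5):

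| Later progression captured | 5% leave | 10% | 15% | 20% |
|---|---|---|---|---|
| None | +2.3 | +4.8 | +7.6 | +10.3 |
| Half | +1.2 | +2.4 | +3.8 | +5.0 |
| All | 0.0 | 0.0 | 0.0 | 0.0 |

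- With a true median of 4 months, the 6-month excess is +1.0 to +5.0 (none captured) or +0.5 to +2.5 (half).
- With n = 20 and a median of 5 months, the 12-month excess is +1.0 to +7.2 or +0.5 to +3.6 (reference about 21.5%, SD 9.1).
- The typical median stays within 0.3 month of the reference in every setting.
- Changing post-progression survival to a median of 8 or 12 months gives +4.6 to +5.0 at 10% leaving and +7.1 to +7.8 at 15%, none captured.

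**What the fix recovers** (n = 41, median 2 months, 15% leaving, none captured, 6-month PFS in %):

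| Contact after exit | Reference | As written | Censor at last assessment | Gap sensitivity |
|---|---|---|---|---|
| 12 months | 14.6 | 22.1 | 16.6 | 13.1 |
| 24 months | 14.9 | 22.3 | 20.1 | 13.4 |

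Share of the bias removed: (22.1 - 16.6) / (22.1 - 14.6) = 5.5 / 7.5 = 73% with 12 months of contact, and (22.3 - 20.1) / (22.3 - 14.9) = 2.2 / 7.4 = 30% with 24 months. The rest remains because deaths after unscanned intervals stand in for earlier, missed progressions.

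**Model dependence.** A second simulation placed leaving at a uniform time before progression would have been detected. It had no deaths and no capture. At a true median of 2 months it gave larger shifts in 6-month PFS: 0.146 to 0.232 at 10% leaving and 0.148 to 0.318 at 20%, with the median unchanged at 3.7 months. At a true median of 4 months and 20% leaving, the estimated median moved from 5.5 to 7.4 months. The direction is the same; the size depends on the model.

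**The case against.** Several points on the other side are sound. PFS carries no threshold, test or named landmark, so the landmark rates above are ones the plan never promises to report. The documents lean towards capturing later progression: there is an Off Study scan, note k of Table 10.1 asks for a scan where possible when clinical progression is suspected, section 11.1.4.3 urges documentation after symptomatic deterioration, and section 6.5 seeks consent for later contact about outcome. The no-capture row is therefore an extreme. At half capture and 5-10% leaving, the excess is +1.2 to +2.4 points against a sampling SD of 5.5. One may also read last contact as the last contact at which the patient was known to be progression-free. That is sensible, but it is not written, and none of the capture provisions sets a censoring date or covers a plain withdrawal.

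A reader might go further and infer that the plan counts patients of unknown status as PFS events. Section 15.3 makes everyone outside the censored group an event, and section 15.4.2 treats response categories 4 to 9, the last being unknown, as failure by progression. The documents do not support that inference. Section 15.4.2 concerns the response rate and nothing extends it to PFS. The residual group in section 15.3 most naturally means patients who progressed or died, the two events just named. The wording leaves the event reading possible, but it is the less natural one.

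The objection that the remedy is incomplete also stands, and the fix is framed accordingly.

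**Conclusion.** The concern holds as a minor point. Followed literally, section 15.3 lets a contact without tumour assessment set the PFS date, which biases the tail of the curve upward whenever later progression is missed. The illustrative size is about +1 to +10 points in 6-month PFS (n = 41, true median 2 months, 5-20% leaving, none to half captured) and zero at full capture. These figures rest on assumed leaving and capture rates and on leaving being independent of prognosis. They are not estimates for this trial.

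It would be wrong to infer that the trial's conclusion is at risk. The rules of 5 of 41 and 7 of 20 responses in section 15.1 do not use PFS.

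**What to change.** In section 15.3:

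1. Censor patients alive without documented progression, including those of unknown status, at the last adequate tumour assessment showing no progression, or at enrollment if there is none. Count off-protocol scans as assessments.
2. Keep all documented progressions and deaths as events in the main analysis.
3. Report beside it one sensitivity analysis that censors, at the last adequate assessment, any event first recorded after two or more missed 8-week assessments.

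The cost is a few sentences and one extra run; the response, off-study and follow-up forms in section 13.1.2 already exist. Leavers contribute shorter follow-up, the curve is slightly lower, and the typical median can fall by up to 0.8 month.

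With n = 41, a median of 2 months, no capture and 5-20% leaving, the revised main analysis is still off by -0.2 to -1.1 points with 6 months of contact, +0.6 to +3.3 with 12 months and +1.5 to +7.5 with 24 months. The sensitivity analysis reads low: -0.3 to -2.0 points with no capture, and -0.8 to -3.7 with full capture if interim scans are not on file. It can lower the median by up to one scan interval, so it belongs beside the main analysis and should not replace it. Informative exit, such as symptomatic deterioration without objective progression, is not resolved by either analysis.

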15.4. Reporting and Exclusions

15.4.1. Evaluation of toxicity.

All subjects who receive at least one dose of study drug (ABT-888 and/or TMZ) will be considered evaluable for toxicity from the time of their first treatment.

Subjects who enroll but do not receive any study treatment will not be considered evaluable for toxicity.

15.4.2. Evaluation of response.

All subjects who register to participate in the study and receive at least one cycle of study drug will be assessed for response to treatment even if there are major protocol treatment deviations or if they are ineligible. Each participant should be assigned one of the following categories: 1) complete response, 2)

partial response, 3) stable disease, 4) progressive disease, 5) early death from malignant disease, 6) early death from toxicity, 7) early death because of other cause, or 9) unknown (not assessable, insufficient data). By arbitrary convention, category 9 usually designates the "unknown" status of any type of data in a clinical database.

All participants who met the eligibility criteria, except those who received no study medication, will be included in the main analysis of the response rate. Participants in response categories 4-9 should be considered to have a treatment failure (disease progression). Thus, an incorrect treatment schedule or drug administration does not result in exclusion from the analysis of the response rate. Patients who did not receive any dose of study drug will not be included in the response evaluation.

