2.1. Study Design

This is a single arm, single stage phase II study to evaluate the efficacy of oral ABT-888 in combination with TMZ for the treatment of metastatic breast cancer. Subjects will receive ABT-888, 30mg PO/dose, every 12 hours on days 1 through 7 of each 28 day cycle. For cycle 1, TMZ will be started at a dose of 150mg/m²/day PO, daily on days 1 through 5 of a 28 day cycle. Measurable tumor will be assessed for response every 8 weeks by standard Response Evaluation Criteria In Solid Tumors. Additional study endpoints include safety assessment and evaluation of clinical benefit rate (CR+PR+SD>16 weeks) and progression free survival. Exploratory correlative studies will also be conducted as described in section 9.1.

This study will be conducted within the Dana-Farber/Harvard Cancer Center only.

A total enrollment of 41 patients is planned. However, patients who enter the study but do not complete 1 cycle of study drugs will not count towards this accrual goal of 41, so a few more patients may be entered.

The study is intended to complete accrual in approximately 18 months with an accrual rate of 2.5 subjects per month.

An expansion cohort of 20 patients with BRCA1 or BRCA2 mutations is planned. Patients who enter the study but do not complete 1 cycle of study drugs will not count towards this accrual goal of 20, so a few more patients may be entered. The expansion cohort is intended to complete accrual in approximately 4 months with an accrual rate of 5 patients per month.

2.2. Primary Objectives (for the primary study and an expansion cohort of BRCA1/2 positive patients)

- To determine the objective response rate (ORR) of ABT-888 and TMZ in metastatic breast cancer.

2.3. Secondary Objectives (for the primary study and an expansion cohort of BRCA1/2 positive patients)

- To further characterize the safety and tolerability of ABT-888 and TMZ in patients with metastatic breast cancer
- To evaluate progression free survival
- To evaluate the clinical benefit rate (CR+PR+SD>16 wks).

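### The sections disagree on who is in the response-rate denominator, and the expansion cohort's 7-response rule is stated only for 20 patients although up to 22 are allowed

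*Combined protocol and SAP*

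**What the plan says.** **Decision rules (section 15.1).** For the primary study: "The combination will be considered worthy of further research if at least 5 of the 41 subjects have a confirmed PR or CR". The stated alpha is 0.05 at a true rate of 5%, and the stated power is 0.93 at 20%. For the expansion cohort: "If at least 7 of the 20 subjects have a confirmed PR or CR the study will be deemed a success". The stated one-sided alpha is 0.025 at 15%, and the stated power is 0.87 at 45%.

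**Accrual and replacement.** Section 2.1: "patients who enter the study but do not complete 1 cycle of study drugs will not count towards this accrual goal of 41"; it says the same for the expansion goal of 20. Section 15.2 defines the 41 as patients who receive at least one cycle and adds: "Subjects who discontinue study participation after enrollment but before receiving one cycle of study drug will be replaced with an additional subject". It makes no exception for progression or death. It also says: "Subjects who receive at least one cycle of study drugs but who never have follow-up tumor measurements done will be counted as non-responders".

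**Evaluable for response (section 11.1.1).** A patient needs measurable disease at baseline, at least one cycle and a re-evaluation of disease. A note adds patients who progress objectively or die before the end of cycle 1.

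**Analysis (section 15.4.2).** The first paragraph says that registered patients with at least one cycle "will be assessed for response to treatment even if there are major protocol treatment deviations or if they are ineligible". The second defines the main analysis: eligible participants, "except those who received no study medication, will be included in the main analysis of the response rate". Response categories 4 to 9, which include early death and unknown, are treatment failures.

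**Expansion size (section 15.2).** "In the expansion cohort a total of approximately 20 patients are planned to be enrolled, with up to 22 allowed". The reason given is rapid accrual near closure, not replacement.

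**The concern.** Both go/no-go rules are fixed response counts set against a fixed number of patients. The reader therefore has to know who is counted, and the sections give different answers for patients who are mostly failures. A team that follows 11.1.1, or that reads the replacement rule as removing patients from the analysis, takes non-responders out of the primary endpoint and reports a higher response rate than the 15.4.2 main analysis would.

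In the expansion cohort the plan allows two sizes for which it prints no rule. Keeping 7 responses at those sizes makes success easier than the stated error rate allows. Section 3.3 says the data from this cohort will be used to support later phase 2 and phase 3 studies in mutation carriers.

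**Working it through.** **1. The sections side by side**

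| Patient | 2.1 and 15.2 | 11.1.1 | 15.4.2 main analysis |
|---|---|---|---|
| Eligible, dosed, progressed or died before completing cycle 1 | Not counted; replaced on stopping | Evaluable | In, as a failure |
| Eligible, dosed, stopped before one cycle for another reason | Not counted; replaced | Not evaluable | In, as a failure if not responding |
| Eligible, one cycle, never re-scanned, no early progression or death | Non-responder | Not evaluable | In, as category 9, a failure |
| Ineligible, one cycle | Counted | Evaluable if re-scanned | Out (but assessed under the first paragraph) |
| Enrolled, never dosed | Replaced | Not evaluable | Out |

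The conflict is in the first three rows. The last row is consistent.

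**2. The plan's own figures**

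Method: exact binomial tail, P(X ≥ r | n, p), with r, n and p from section 15.1.

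- Primary: P(X ≥ 5 | 41, 0.05) = 0.0525 and P(X ≥ 5 | 41, 0.20) = 0.934. Stated: 0.05 and 0.93.
- Expansion: P(X ≥ 7 | 20, 0.15) = 0.0219 and P(X ≥ 7 | 20, 0.45) = 0.870. Stated: 0.025 and 0.87.

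At exactly 41 and 20 both rules perform as printed, to rounding; the expansion rule's attained alpha is within its stated level.

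**3. Expansion cohort at the other permitted sizes**

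| n | Responses required | Alpha at 15% | Power at 45% |
|---|---|---|---|
| 20 | 7 | 0.0219 | 0.870 |
| 21 | 7 | 0.0287 | 0.904 |
| 22 | 7 | 0.0368 | 0.929 |
| 21 | 8 | 0.0083 | 0.803 |
| 22 | 8 | 0.0114 | 0.848 |

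With 7 kept, alpha exceeds 0.025 at both 21 and 22. With 8 it stays below 0.025, but power falls below 0.87. These figures apply if all 21 or 22 patients are in the denominator.

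**4. Primary study with added dosed patients**

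A dosed patient who stopped before one cycle is a near-certain non-responder. Under section 11, disease is re-evaluated every 2 cycles and a response must be confirmed at least 4 weeks later. If 5% and 20% are the rates among the 41 one-cycle patients, adding certain failures leaves the chance of 5 or more responses at 0.0525 and 0.934. What moves is the estimate and its interval:

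- 5/41 = 12.2%, exact 90% CI 4.9 to 23.9%.
- 5/45 = 11.1%, exact 90% CI 4.5 to 22.0%.

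Only if the design rates are taken to hold for every dosed patient does alpha itself rise: P(X ≥ 5 | 42, 0.05) = 0.057 and P(X ≥ 5 | 45, 0.05) = 0.073. The values 42 and 45 are assumptions. Section 2.1 says only that a few more patients may be entered, and no replacement rate is given.

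In the other direction, one ineligible patient among the 41 gives n = 40, with alpha 0.048 and power 0.924.

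**The case against.** The strongest reply is that the governing set is already named. Section 15.4.2 is the only place that defines a main analysis of the response rate, section 2.1 speaks of an accrual goal, and the replacement sentence in 15.2 governs enrolment. Sections 15.2 and 15.4.2 also agree that an unscanned one-cycle patient is a failure. The two paragraphs of 15.4.2 can be read together, since being assessed for response is not the same as being in the main analysis. This carries weight, and it is why the 15.4.2 set is the natural one to adopt. It does not remove the conflict: 11.1.1 still drops the unscanned patient, and 15.2 ties the 41 on which the 5-response rule rests to one-cycle patients, a different set.

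A second reply is that the expansion effect is small and contingent. The cohort is non-comparative, 22 is only a ceiling, and 0.037 is still below the 0.05 used in the primary study. That is fair as to size. The plan nevertheless states 0.025 and gives no rule for sizes that it permits.

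Two stronger readings are tempting and should not be drawn:

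- A reader might infer that replacements inflate the primary study's alpha to 0.057 or 0.073. That holds only if the design rates apply to all dosed patients; near-certain failures do not raise it.
- A reader might infer from section 3.3, which reports 4 responses in the first 41 enrolled (4 of 8 carriers, none of the other 33), that the choice of denominator could decide the primary result. Four responses miss a cut-off of 5 at every n. Changing the outcome would take a further response, not another denominator.

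**Conclusion.** The concern holds as an inconsistency that should be fixed. Sections 2.1, 11.1.1, 15.2 and 15.4.2 do not define one response-rate denominator, and the narrower readings leave out failures. In the primary study the consequence is mainly a somewhat higher reported rate and a shifted interval: about one percentage point between 41 and an assumed 45 with five responders. The number of patients affected cannot be known from the documents.

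The clearest numerical consequence is in the expansion cohort. If 21 or 22 patients are analysed and 7 responses still count as success, one-sided alpha is 0.029 or 0.037 against the stated 0.025, with power 0.90 or 0.93. If the patients above 20 are replaced non-completers who are not counted, the printed rule still applies; 15.2 does not say whether its 22 includes them.

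**What to change.** 1. **One denominator.** State that the 15.4.2 main-analysis set (eligible, any dose) is the denominator for the reported response rate and its interval in both cohorts, and align 2.1, 11.1.1 and 15.2 with it. Count everyone in it without a confirmed CR or PR as a non-responder. Report ineligible treated patients separately, with the number of and reasons for replacements. Keep the one-cycle set as a sensitivity analysis.

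2. **Primary study.** Leave the cut-off at 5. Preliminary responses are already known, so it should not be changed now.

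3. **Expansion cohort, before its data are seen.** Choose one of the following, and state whether the 22 includes replaced patients:
   - Name the 20 patients who decide the 7-response rule. One choice is the first 20 by registration order who count towards the accrual goal in 2.1, with all eligible dosed patients in the reported rate and interval.
   - Require 8 responses at 21 or 22 (alpha and power 0.008 and 0.80, or 0.011 and 0.85).
   - Keep 7 and restate alpha and power as 0.029 and 0.90 at 21, and 0.037 and 0.93 at 22.

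**Cost.** Aligned wording in four sections, a sentence or two on the expansion rule and one sensitivity analysis; no extra patients. The reported response rate will be slightly lower. Power falls to 0.80 or 0.85 if 8 responses are required. It also falls if the first 20 patients with any dose, rather than the first 20 who count under 2.1, decide. If one or two of those stop before one cycle and 45% applies to completers, P(X ≥ 7 | 19, 0.45) = 0.83 and P(X ≥ 7 | 18, 0.45) = 0.77.
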